APPENDIX D: RISK-INJURY-FAILURE-LOSS-END-STAGE RENAL DISEASE CRITERIA

Table 8. Definition of Risk-Injury-Failure-Loss-End-Stage Renal Disease Criteria

Term	Definition
Risk (R)	Increased creatinine $1.5 \times$ or GFR decrease $>25\%$
Injury (I)	Increased creatinine $2 \times$ or GFR decrease $>50\%$
Failure (F)	Increased creatinine level $3 \times$, GFR decrease $>75\%$, or creatinine level ≥ 4 mg/dL
Loss (L)	Persistent acute renal failure or complete loss of function for >4 weeks
ESKD (E)	ESKD for >3 months
ESKD = end-stage kidney disease; GFR = glomerular filtration rate. Source: Hartzell JD, Neff R, Ake J, et al. Nephrotoxicity associated with intravenous colistin (colistimethate sodium) treatment at a tertiary care medical center. Clin Infect Dis. 2009;48(12):1724-1728

**LIST OF ABBREVIATIONS**

Abbreviation	Definition
ADA	Anti-phage antibodies
ADaM	Analysis Data Model
AE	Adverse event
AKI	acute kidney injury
ATC	Anatomical therapeutic chemical
BAT	Best available therapy
CDISC	Clinical Data Interchange Standards Consortium
CEAC	Clinical Efficacy Adjudication Committee
CI	Confidence interval
CRP	C-reactive protein
CVPU	Confusion, Voice, Pain, Unresponsive
eCRF	Electronic case report form
CSR	Clinical Study Report
DRC	Data Review Committee
EOS	End of Study
EOT	End of Treatment
ESKD	End-stage kidney disease
ICU	Intensive care unit
ITT	Intent-to-Treat
IV	Intravenous
MAD	Multiple ascending dose
MedDRA	Medical Dictionary for Regulatory Activities
MITT	Microbiological Intent-to-Treat
MRSA	Methicillin-resistant Staphylococcus aureus
MSSA	Methicillin-susceptible Staphylococcus aureus
NCI CTCAE	National Cancer Institute Common Terminology Criteria
NEWS2	National Early Warning Score 2
PFU	Plaque-forming units
PK	Pharmacokinetics
RIFLE	Risk-Injury-Failure-Loss-End-stage renal disease
PT	Preferred term
Q6h	Every 6 hour
SA	Staphylococcus aureus
SAB	Staphylococcus aureus bacteremia
SAE	Serious adverse event
SAP	Statistical Analysis Plan
SDTM	Study Data Tabulation Model
SOC	System organ class
SpO 2	Oxygen saturation
TEAE	Treatment-emergent adverse event
TFLs	Tables, Figures and Listings
TOC	Test of Cure
WHO	World Health Organization

## 1 INTRODUCTION

The purpose of this Statistical Analysis Plan (SAP) is to provide a description of the statistical methods to be implemented for the analysis of data from the study with protocol number AP-SA02-101. The SAP will be finalized prior to database lock. Any deviations from the SAP after database lock will be documented in the final Clinical Study Report (CSR).

## 2 STUDY OVERVIEW

### 2.1 Study Objectives

#### 2.1.1 Phase 1b

The objective of Phase 1b is to evaluate the safety and tolerability of multiple ascending intravenous (IV) doses of AP-SA02 or placebo as an adjunct to best available therapy (BAT) compared to BAT alone in subjects with *Staphylococcus aureus* (SA) bacteremia (SAB).

#### 2.1.2 Phase 2a

The objective of Phase 2a is to evaluate the efficacy, safety, and tolerability of multiple doses of AP-SA02 or placebo as an adjunct to BAT compared to BAT alone in subjects with complicated SAB.

### 2.2 Study Design

#### 2.2.1 Overview

This is a first-in-human, prospective, Phase 1b/2a, randomized, double-blind, placebo-controlled, multiple ascending dose (MAD) study to assess the safety, tolerability, and efficacy of multiple IV doses of AP-SA02 as an adjunctive therapy to BAT and compared to BAT alone for the treatment of SAB. This multiple dose escalation design will assess the safety and tolerability, as well as the efficacy, of various dosing cohorts with phage pharmacokinetics (PK) to identify a dose and duration of dosing that offers the best therapeutic potential benefit.

In Phase 1b, a standard MAD design for safety and tolerability will begin by randomizing subjects in Phase 1b Cohort 1 to receive either approximately  $2 \times 10^9$  plaque-forming units (PFU) or placebo in addition to BAT. A Data Review Committee (DRC) will convene to review the data from Phase 1b Cohorts and during Phase 2a, as needed. The DRC will review emerging safety data throughout the study to determine if it is safe and appropriate to continue the study with the currently planned dose levels for the subsequent cohorts, or if further refinement of the proposed dose levels or dosing duration is warranted. The planned dose levels and dosing duration after Phase 1b Cohort 1 may be modified and/or additional cohorts may be added based on emerging information from the current study as well as other ongoing studies. The highest total daily dose will not exceed  $8 \times 10^{11}$  PFU and no more than 40 additional subjects will be added without a protocol amendment. The DRC will also determine how to advance the cohorts (serially or simultaneously). The DRC can receive unblinded data, if requested and deemed necessary to adequately complete their review. Further details regarding the role, responsibilities, and procedures of the DRC will be provided in the DRC Charter.

The planned enrollment in each of the Phase 1b cohorts is 4 subjects per cohort (AP-SA02 to placebo 3:1); however, this may be modified after DRC review. Subjects in Phase 1b Cohort 1 will receive IV bolus infusion doses of blinded study drug every 6 hours for 5 study days (a total of 20 doses) in an inpatient location in addition to BAT. Following 5 days of dosing with study drug, additional study visits will be conducted at the End of Treatment (EOT) for study drug (Day 5), at the Test of Cure (TOC) for

study drug (Day 12), TOC for BAT (7 days [ $\pm 1$  day] after the end of BAT), and at End of Study (EOS) (28 days after the end of BAT). Subsequent cohorts (e.g., planned Phase 1b Cohort 2 or additional cohorts [up to 3]) will proceed similarly; however, the duration of dosing may be modified after the DRC review of the preceding cohort.

Study procedures will follow the Schedule of Procedures ([Appendix A](#)).

In Phase 2a, approximately 42 subjects will receive IV bolus infusion doses of blinded study drug every 6 hours, for no more than 14 days as determined by analysis during or after Phase 1b, in addition to BAT. Following 5 days of dosing with study drug, additional study visits will be conducted at EOT for study drug (Day 5), TOC for study drug (Day 12), TOC for BAT (7 days [ $\pm 1$  day] after the end of BAT), and EOS (28 days after the end of BAT). If the study drug EOT is extended after the DRC review, the study drug TOC visit will occur 7 days after the last day of dosing and the study drug EOS visit will occur 28 days after the end of BAT.

The following dose cohorts are planned:

#### Phase 1b

- Cohort 1 (AP-SA02 to placebo 3:1):
  - Planned approximately  $2 \times 10^9$  PFU ( $1 \times 10^9$  PFU/phage) administered via IV bolus infusion every 6 hours for a period of 5 days;
- Cohort 2 (AP-SA02 to placebo 3:1):
  - Planned approximately  $2 \times 10^{10}$  PFU ( $1 \times 10^{10}$  PFU/phage) administered via IV bolus infusion every 6 hours for a period of 5 days; and

Note: The dose, frequency, and duration may be modified after DRC review. Maximum dosing duration will be no more than 14 days.

Additional cohort(s) (up to 3) as determined after DRC review.

#### Phase 2a

- Phase 2a (AP-SA02 to placebo 2:1):
  - Dose and duration are to be determined based on safety and tolerability from or after Phase 1b, administered via IV bolus infusion.

Note: The dose, frequency, and duration may be modified after DRC review. Maximum dosing duration will be no more than 14 days.

A DRC will be convened to review all blinded safety data through TOC for study drug (Day 12) to recommend dose escalation. Safety stopping rules, including the number of dose-limiting toxicities, are prespecified in [Section 4.3 of protocol](#). The DRC can receive unblinded data, if requested and deemed necessary to adequately complete their review. Upon completion of Phase 1b Cohort 2, Phase 2a may be initiated and may be an expansion of one of the previous cohorts.

In Phase 2a, subjects will be randomized in a 2:1 ratio to receive AP-SA02 or placebo. Randomization will be stratified by methicillin susceptibility/resistance. Subjects will be on BAT for a minimum of 28 days to 56 days (complicated SAB) and followed through 28 days after the end of BAT, for a total of 56 to 84 days in the study. The BAT must be planned for a minimum of 28 days and a maximum of 56 days, inclusive of the days on BAT started prior to study enrollment/randomization. The EOT for BAT will be defined based on the prespecified duration of therapy at the time of enrollment. The prespecified duration

of BAT at Screening may be increased within 7 days after randomization with duration of BAT no more than 56 days in the event that new/additional clinical information warrants a longer duration of therapy; this must be documented in the subject's source chart and electronic case report form (eCRF). All changes made to the subject's BAT and the reason for such changes must be documented on the appropriate eCRF.

### 2.2.2 Randomization and Blinding

Subjects in Phase 1b will be randomized in a 3:1 ratio in a blinded manner to receive AP-SA02 or placebo. For Phase 2a, subjects will be randomized in a 2:1 ratio in a blinded manner to receive AP-SA02 or placebo.

Subjects will be randomized using a centralized randomization system, according to a computer-generated randomization list, and stratified by methicillin susceptibility/resistance for Phase 2a only. Dosing should occur as soon as possible after randomization. Treatment group assignment will be blinded to the subjects, site study team, Sponsor study team, Contract Research Organization study team, and Investigators.

### 2.2.3 Study Drug

AP-SA02 is a proprietary multi-phase therapeutic candidate. [REDACTED]

Placebo will be a sterile dilution buffer used for active AP-SA02. [REDACTED]

AP-SA02 or placebo will be administered via IV bolus infusion every 6 hours for 5 consecutive days in an inpatient location. In addition, all subjects will receive at least 14 days (uncomplicated SAB) or 28 days (complicated SAB) and up to 56 days of BAT. BAT will be administered at the discretion of the Investigator.

### 2.2.4 Sample Size Determination

The study will enroll approximately 50 eligible subjects. Enrollment may be expanded up to a total of approximately 100 subjects to ensure that at least 8 treated and 4 placebo Phase 2a subjects are MRSA subjects and to account for additional subjects and cohorts that may be enrolled based on DRC review and Sponsor input based on emerging data. To ensure that at least 8 treated and 4 placebo Phase 2a subjects are MRSA subjects, no more than approximately 70 non-MRSA subjects will be enrolled without a protocol amendment.

The Phase 1b MAD safety cohorts will follow a standard 3 + 1 design for 2 cohorts (n = 4 for each cohort for a total of 8 subjects). However, additional cohorts (up to 3) may be added or existing cohorts expanded per recommendation of the DRC or Sponsor decision. The total sample size in Phase 1b may be increased up to a total of 20 subjects without a protocol amendment in consultation with the DRC.

Phase 2a will have an initial sample size of approximately n = 42 with a study drug to placebo allocation of 2:1 in order to enroll at least 38 subjects meeting the Microbiological Intent-to-Treat (MITT) Population criteria with the assumption that approximately 90% of randomized subjects will satisfy the MITT Population criteria. This will provide at least 80% power to detect a difference of 50% in the proportion of subjects in each treatment arm, with a 30% placebo portion meeting all conditions for Clinical Improvement or response at TOC for study drug (Day 12) in the MITT Population with a type 1 error rate of 0.05 (1-sided) using Fisher's exact test. Additional subjects may be included in Phase 2a after a protocol amendment.

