3.1 Summary of Study Design

[figure not shown]
This is a first-in-human, prospective, Phase 1b/2a, randomized, double-blind, placebo-controlled, multiple ascending dose (MAD) study to assess the safety, tolerability, and efficacy of multiple IV doses of AP-SA02 as an adjunctive therapy to BAT and compared to BAT alone for the treatment of SAB. This multiple dose escalation design will assess the safety and tolerability, as well as the efficacy, of various dosing cohorts with phage PK to identify a dose and duration of dosing that offers the best therapeutic potential benefit.

In Phase 1b, a standard MAD design for safety and tolerability will begin by randomizing subjects in Phase 1b Cohort 1 to receive either approximately 2×10^9 plaque-forming units (PFU) or placebo in addition to BAT. A DRC will convene to review the data from Phase 1b Cohorts and during Phase 2a, as needed. The DRC will review emerging safety data throughout the study to determine if it is safe and appropriate to continue the study with the currently planned dose levels for the subsequent cohorts, or if further refinement of the proposed dose levels or dosing duration is warranted. The planned dose levels and dosing duration after Phase 1b Cohort 1 may be modified and/or additional cohorts may be added based on emerging information from the current study as well as other ongoing studies. The highest total daily dose will not exceed 8×10^{11} PFU and no more than 40 additional subjects will be added without a protocol amendment. The DRC will also determine how to advance the cohorts (serially or simultaneously). The DRC can receive unblinded data, if requested and deemed necessary to adequately complete their review. Further details regarding the role, responsibilities, and procedures of the DRC will be provided in the DRC Charter.

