9.2.1 Analysis of Phase 2a Endpoints

Phase 2a endpoints will be summarized descriptively for each treatment arm using appropriate proportions and means depending on the data type along with the 95% confidence interval. No formal hypothesis testing is planned.

Additional details will be described in the SAP.

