9.2.6 Sample Size Determination

The study will enroll approximately 50 eligible subjects. Enrollment may be expanded up to a total of approximately 100 subjects to ensure that at least 8 treated and 4 placebo Phase 2a subjects are MRSA subjects and to account for additional subjects and cohorts that may be enrolled based on DRC review and Sponsor input based on emerging data. To ensure that at least 8 treated and 4 placebo Phase 2a subjects are MRSA subjects, no more than approximately 70 non-MRSA subjects will be enrolled without a protocol amendment.

The Phase 1b MAD safety cohorts will follow a standard 3 + 1 design for 2 cohorts ($n = 4$ for each cohort for a total of 8 subjects). However, additional cohorts (up to 3) may be added or existing cohorts expanded per recommendation of the DRC or Sponsor decision. The total sample size in Phase 1b may be increased up to a total of 20 subjects without a protocol amendment in consultation with the DRC.

Phase 2a will have an initial sample size of approximately $n = 42$ with a study drug to placebo allocation of 2:1 in order to enroll at least 38 subjects meeting the MITT Population criteria with the assumption that approximately 90% of randomized subjects will satisfy the MITT Population criteria. This will provide at least 80% power to detect a difference of 50% in the proportion of subjects in each treatment arm, with a 30% placebo portion meeting all conditions for Clinical Improvement or response at TOC for study drug (Day 12) in the MITT Population with a type 1 error rate of 0.05 (1-sided) using Fisher's exact test. Additional subjects may be included in Phase 2a after a protocol amendment.

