### 3.1.4 Hypothesis Testing

No formal testing will be done.

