Clinical improvement or response (meets all criteria on [Table 2](#) in [section 7.3 of protocol](#)) at TOC for study drug (Day 12), TOC for BAT (7 days  $\pm 1$  day] after the end of BAT) and EOS (28 days after the end of BAT) will be assessed by both investigator and Clinical Efficacy Adjudication Committee (CEAC).

Based on both investigator and CEAC assessments, proportion of subjects who experience clinical improvement or response will be provided. Chi-square test p-value will be provided for clinical improvement or response to compare AP-SA02 and placebo.

The proportions of responders (including clinical improvement or response) will be plotted by AP-SA02 and placebo at TOC for study drug (Day 12), TOC for BAT (7 days [ $\pm 1$  day] after the end of BAT) and EOS (28 days after the end of BAT) by both investigator and CEAC.

Microbiological outcome at Day 5, Day 7, TOC for study drug (Day 12), TOC for BAT, and EOS will be determined programmatically based on blood culture results tested by local microbiology laboratories per [Table 3](#) as 1 of the outcomes: Eradication, Presumed eradication, Persistence, Presumed persistence, Recurrence. The microbiological outcome at Day 5, Day 7, TOC for study drug (Day 12), TOC for BAT, and EOS will be summarized with counts and percentages of subjects based on categories in [Table 3](#).

The Chi-square test p-value will be provided for the counts of microbiological eradication (including presumed eradication) and microbiological persistence (including presumed persistence) compare AP-SA02 and placebo.

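### Phase 2a is powered for a one-sided Fisher test that the analysis plan does not list; the SAP disclaims formal testing yet requires about 56 unlabelled between-arm p-values per comparison

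*SAP*

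**What the plan says.** **Sizing.** SAP 2.2.4 and Protocol 9.2.6 give the same basis: about 42 randomized 2:1, about 90% of them in the MITT Population (at least 38), a 30% placebo response, a 50-point difference, and at least 80% power in the "MITT Population with a type 1 error rate of 0.05 (1-sided) using" Fisher's exact test. The endpoint is clinical improvement or response at test of cure for study drug (Day 12).

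**Testing policy.** Protocol 9.2.1 has the Phase 2a endpoints summarized "using appropriate proportions and means depending on the data type along with the 95% confidence interval. No formal hypothesis testing is planned". SAP 3.1.4 says "No formal testing will be done".

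**What the SAP then specifies.** In SAP 3.4.1, clinical response at three visits "will be assessed by both investigator and Clinical Efficacy Adjudication Committee (CEAC"), and a "Chi-square test p-value will be provided for clinical improvement or response to compare AP-SA02 and placebo". Sections 3.4.1 and 3.6 ask for further between-arm p-values from chi-square tests, Cox models and t-tests. Section 3.7.1 adds chi-square p-values for adverse events by system organ class and preferred term.

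**Hierarchy.** Phase 2a has a flat endpoint list (Protocol 7.2, SAP 2.3.2). The only endpoint called primary is Phase 1b safety. SAP 3.4 says that the 3.4.1 endpoints may be assessed as secondary.

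**Population.** MITT in Protocol 9.1 requires baseline bacteremia and at least 1 dose. The SAP's only MITT set (3.2.2, Per Protocol MITT) requires at least 4 initial doses.

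**Enrolment.** Protocol 3.1 says "no more than 40 additional subjects will be added without a protocol amendment". Protocol 9.2.6 allows about 100 in total and up to 20 in Phase 1b, and adds: "Additional subjects may be included in Phase 2a after a protocol amendment".

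**The concern.** A power statement has meaning only for a specified comparison: endpoint, assessor, population, test, sidedness and alpha. Here the endpoint and visit survive into the SAP. The test, sidedness and alpha do not, the assessor is doubled, and the population is redefined. A reader of the study report could not say which result the 80% refers to.

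Meanwhile a plan described as descriptive yields a long list of p-values with no status attached, so a favourable one could be given weight after the fact. SAP section 6 discloses the changed population definitions. It does not disclose the added p-values or the missing intervals for proportions. With about 42 subjects, an interval for the risk difference is the most informative summary, and it is the one left out.

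**Working it through.** **1. Reproduce the stated power.** Inputs (SAP 2.2.4): 42 × 0.90 = 37.8, so 38 evaluable; 2:1 gives 25:13; response 30% + 50 points = 80% vs 30%; one-sided Fisher at 0.05.

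Power = Σ over (a, b) of Bin(a; 25, 0.80) × Bin(b; 13, 0.30) × 1{p(a, b) ≤ 0.05}, where p is the upper hypergeometric tail.

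| Split | One-sided Fisher 0.05 | Two-sided Fisher 0.05 | Two-sided chi-square 0.05, uncorrected |
|---|---|---|---|
| 25:13 | 87.8% | 83.8% | 88.6% |
| 26:12 | 86.3% | 81.2% | 86.4% |
| 28:14 | 90.8% | 86.8% | 91.4% |

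The claim of at least 80% is correct as a lower bound.

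**2. Count the between-arm p-values for one two-arm comparison.**

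| Endpoint | Visits or models | p-values |
|---|---|---|
| NEWS2 time to event (Cox) | 1 | 1 |
| NEWS2 responders | Days 2, 3, 4, 5, 7, 12 | 6 |
| NEWS2 change from baseline | Days 2–7 and 12 | 7 |
| Clinical response | 3 visits × 2 assessors | 6 |
| Microbiological outcome | 5 visits | 5 |
| Focal signs; late composite; death | 1 each | 3 |
| Failure or relapse | 3 visits | 3 |
| Discharge and discharge readiness | 1 each | 2 |
| ICU need; ICU duration | 1 each | 2 |
| Mechanical; noninvasive ventilation need | 1 each | 2 |
| **SAP 3.4.1 subtotal** | | **37** |
| Resolution of bacteremia; signs of bacteremia (Cox) | 1 each | 2 |
| CRP change | 9 visits | 9 |
| IL-10 change | 8 visits | 8 |
| **SAP 3.6 subtotal** | | **19** |
| **Total** | | **56** |

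The Day 1 CRP and IL-10 draws count as post-baseline because they follow the second infusion. Excluding both gives 54. Counting Day 1 NEWS2 (+1) and testing eradication and persistence separately at five visits (+5) gives 62. Paired within-arm t-tests, safety p-values and the additional populations in SAP 3.4 are not counted.

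Expected number below 0.05 under no effect: 56 × 0.05 = 2.8. This expectation holds, approximately, whatever the correlation between endpoints.

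**3. Chi-square in a sparse table.** Take 0/28 vs 2/14.
- Pearson: χ² = 42 × (0×12 − 2×28)² / (28 × 14 × 2 × 40) = 131,712 / 31,360 = 4.20, p = 0.040.
- Fisher: C(14,2)/C(42,2) = 91/861 = 0.106. The only other table that is neither more balanced nor more likely does not exist, so the two-sided value is the same.

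For the powered endpoint the issue is small: the largest true size of the nominal 5% chi-square at 25:13 is about 5.4%, and it is 5.3% at a 30% response rate.

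**4. Precision if the plan stays descriptive.** Wald half-width at 25:13, 80% vs 30%: 1.96 × √(0.80×0.20/25 + 0.30×0.70/13) = 1.96 × √(0.00640 + 0.01615) = 0.294, about ±29 points.

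**5. Test and interval must match.** At 20/25 vs 6/13, one-sided Fisher gives p = 0.040, significant at one-sided 5% but not at the one-sided 2.5% to which a 95% interval corresponds.

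**6. Enrolment limits.** Planned: 8 + 42 = 50. Adding 40 without amendment gives 90, not about 100. The phase limits that need no amendment give 20 + 42 = 62, below even the limit of about 70 non-MRSA subjects.

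**The case against.** **P-values under a no-formal-testing clause are naturally read as nominal, and this is an early-phase trial.** That is fair, and it limits the defect to a missing label and a missing hierarchy. It does not explain why a type 1 error rate is stated at all, or why the protocol's intervals were dropped for proportions.

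**The powered endpoint is still compared between arms at Day 12.** This stands. The listed chi-square has 88.6% power at 25:13, so a reader who infers that the trial is underpowered, or that the power figure is wrong, would be mistaken on the documents' own assumptions.

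**Neither document rules out Fisher's test by name.** This also stands. They disclaim formal testing in general, and Fisher simply does not appear in the analysis sections.

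**The count includes many repeated measures.** It does: 7 + 9 + 8 = 24 of the 56 are by-day t-tests on NEWS2, CRP and IL-10. The figure describes volume, not 56 separate claims.

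**Chi-square harm is easy to exaggerate.** A reader might infer a materially inflated error rate for the powered comparison; 5.4% at most does not support that. Nor do the documents call for MRSA subgroup p-values, since SAP 3.4.2 specifies no test. The harm lies in rare-event tables: ICU and ventilation need, and adverse events by preferred term.

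**The enrolment limits might suggest that an MRSA top-up of Phase 2a is forbidden.** The text does not say so. It permits additions after an amendment and does not state that the total of about 100 is amendment-free. Whether a top-up will be needed depends on MRSA prevalence, which the documents do not give.

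**Conclusion.** The point holds. The sample size itself is sound on its stated assumptions (80% vs 30%, 25:13 evaluable), but the power statement is not carried through to one specified analysis: test, sidedness and alpha are absent from the analysis sections, two assessors have equal standing, and the population requires more doses than the one powered. About 56 between-arm p-values (54 to 62 by reading) have no declared status. Chi-square is a poor choice for the sparse tables, and the protocol's 95% intervals are missing for proportions. These matter for how results are reported and read, not for whether the trial is large enough. The enrolment limits are a separate wording inconsistency.

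**What to change.** 1. **SAP 3.1.4 and 3.4.1, choose one.**
   - Name Day 12 clinical response as the single powered comparison. State one assessor (investigator or adjudication committee, the sponsor's choice), the population used in the power statement, Fisher's exact test, its alpha and its sidedness. Give a matching interval for it: a two-sided 90% interval for a one-sided 5% test. Alternatively, restate the test as two-sided 5% Fisher, with power 83.8% at 25:13, and keep 95%.
   - Or keep the plan descriptive, delete the power claim and state the expected interval width (about ±29 points).
2. Replace chi-square by Fisher's exact test for sparse tables.
3. Report risk differences with 95% confidence intervals for all binary endpoints, as Protocol 9.2.1 leads the reader to expect.
4. Label all other p-values nominal, or drop them, and record the departure from the protocol in SAP section 6.
5. Separately, reconcile the enrolment limits in Protocol 3.1 and 9.2.6 and SAP 2.2.1 and 2.2.4, saying which apply without an amendment.

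The cost is wording and table shells. No extra subjects or data are needed. Some p-values will be less favourable under Fisher, and there may be fewer of them to display.
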